The safety of ABT-263 has been evaluated in single- and repeat-dose (up to 6 and 9 months in duration in rats and dogs, respectively), reproductive (male and female fertility and embryo fetal development), safety pharmacology (cardiovascular, neurofunctional, and pulmonary), genetic (Ames, in vitro cytogenetics, and in vivo micronucleus), and special studies (guinea pig sensitization; lymphocyte immunophenotyping; and single-dose oral toxicity in male rats). The primary effects of ABT-263 were on the hematopoietic system (platelets and lymphocytes) and the male reproductive system (germ cell depletion), and are believed to be based on inhibition of one or more members of the Bcl-2 family of antiapoptotic proteins. Other findings included ovarian atrophy (rats only), and generally minimal and reversible liver changes (single-cell hepatocellular necrosis, increased mitotic index, and hypertrophy/hyperplasia and pigmentation of Kupffer cells) and single-cell necrosis in various tissues. ABT-263 was neither genotoxic, nor did it affect male or female fertility in rats or embryo-fetal development in rats and rabbits. ABT-263-related effects were observed on brain, testes, and circulating platelets in juvenile rats. Effects on the brain (cerebellar hypoplasia), which were not observed in adult rats, were the likely result of incomplete maturation of the blood-brain-barrier at the time dosing was initiated in the rat pups (post natal Day 7).

ABT-263 caused increases in pulmonary and peripheral vascular resistance and decreases in cardiac output in the dog following acute or multiple daily dosing. Despite the increases in vascular resistance, there were no increases in blood pressure. On Day 28 of the oral dosing study, these cardiovascular effects were associated with a mean C_{\max} value of 16.6 $\mu\text{g/mL}$, whereas no statistically significant hemodynamic changes were associated with a mean C_{\max} of 11.4 $\mu\text{g/mL}$.¹³ Similar systemic exposures induced these effects in the acute cardiovascular study.

Chronic Lymphocytic Leukemia (CLL)

Chronic lymphocytic leukemia (CLL) is a monoclonal disorder characterized by a progressive accumulation of functionally incompetent lymphocytes. It is the most

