 - s. For subjects who continue in the Extension Study, the Final Visit and 30 Day Safety Follow-Up Visit procedures will be performed upon completion of the Extension Study. Refer to [Appendix G](#) for the Schedule of Assessments for subjects enrolled in the Extension Study.
- Note: A schedule of assessments for subjects enrolled in Phase 1 can be found in [Table 1](#) and [Table 2](#). Pharmacokinetic (PK) collection time points for Phase 1 are located in [Table 4](#) and [Table 5](#). PK collection time points for Phase 2a are located in [Table 6](#). Biomarker collection time points for Phase 1 are in [Table 8](#). Biomarker collection time points for Phase 2a are located in [Table 9](#).
-

Table 4. Schedule of Blood Collection for ABT-263 Assay (Pharmacokinetic Sampling) – Phase 1, Cycle 1

Phase	Cycle 1 Day 1	Cycle 1 Day 2	Cycle 1 Day 14
Phase 1 – 14/21 day schedule	0 (pre-dose) 2, 4, 6, 8 hours post-dose	24 hours post-dose Day 1 (pre-dose Day 2)	0 (pre-dose) 2, 4, 6, 8 hours post-dose
Phase 1 – 21/21 day schedule – with lead-in	0 (pre-dose) 2, 4, 6, 8 hours post-dose	24 hours post-dose Day 1 (pre-dose Day 2)	0 (pre-dose) 2, 4, 6, 8 hours post-dose

All 0 hour (pre-dose) PK samples will be collected around the same time for platelet sample collection.

Note: In addition, serial pharmacokinetic samples will be obtained from subjects who develop Grade 4 thrombocytopenia ($< 25,000/\text{mm}^3$). The first pharmacokinetic sample should be collected as soon as possible after determination of the Grade 4 thrombocytopenia and then 24 and 48 hours thereafter.

Table 5. Schedule of Blood Collection for ABT-263 Assay (Pharmacokinetic Sampling) – Phase 1, Cycle 2 and Beyond

Phase	Cycle 2 Day 3	Cycle 2 Day 8	Cycle 2 Day 14	Cycle 3 Day 1	Cycle 3 Day 14	Day 14 of Cycles 6, 9, 12 and 15
Phase 1 – 14/21 day schedule	0 hour (pre-dose)	0 hour (pre-dose)	0 hour (pre-dose)	4 to 8 hours post-dose (immediately after ECG)	0 hour (pre-dose) and 4 to 8 hours post-dose (immediately after ECG)	0 (pre-dose)
Phase	Cycle 2 Day 3	Cycle 2 Day 8	Cycle 2 Day 14	Cycle 3 Day 1	Cycle 3 Day 14	Day 1 of Cycles 6, 9, 12 and 15
Phase 1 – 21/21 day schedule – with lead-in	0 hour (pre-dose)	0 hour (pre-dose)	0 hour (pre-dose)	4 to 8 hours post-dose (immediately after ECG)	0 hour (pre-dose) and 4 to 8 hours post-dose (immediately after ECG)	0 (pre-dose)

All 0 hour (pre-dose) PK samples will be collected around the same time for platelet sample collection.

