Body temperature (oral or tympanic), blood pressure and pulse will be measured at Screening, Day 1 of Cycle 1, weekly through the first 2 cycles, Day 1 of each subsequent cycle (or within 72 hours prior), at the Final Visit and at the Safety Follow-up Visit. During the lead-in period (21/21 day dosing schedule), body temperature (oral), blood pressure and pulse will also be measured at Lead-in Day 1. The vital signs measurements at Screening will serve as the baseline measurements for clinical assessment. For the Extension Study, body temperature, blood pressure and pulse will be measured at Day 1, every 4 cycles (e.g., Cycle 4 Day 1, Cycle 8 Day 1, etc.), Final Visit and at the Safety Follow-up Visit.

In Phase 1, blood pressure and pulse rate will be measured approximately 30 to 60 minutes after study drug administration.

Blood pressure and pulse rate will be measured after the subject has been sitting for at least 5 minutes on days study drug is administered in the clinic.

COVID-19 Pandemic-Related Acceptable Protocol Modifications

Due to the COVID-19 pandemic, subject visits may be conducted via phone or video conference. In these situations, weight, and vital signs measurements may be performed by the subject or caregiver as needed.

Platelet Count

The platelet count measurement obtained on Cycle 1 Day 1 (pre-dose) will serve as the baseline for clinical assessment for the 14/21 day dosing schedule. The platelet count measurement obtained on Lead-in Day 1 (pre-dose) will serve as the baseline for clinical assessment for the 21/21 day dosing schedule with lead-in period.

If platelet count on any given day is less than 50,000/mm³, additional platelet counts should be performed every day or at the discretion of the investigator.

If a platelet transfusion is deemed necessary, a post-transfusion platelet count should be obtained within 10 to 60 minutes.

Platelet counts < 25,000/mm³ should be confirmed the same day by manual reading and a separate peripheral draw. Additional platelet counts will be obtained from a subject if ABT-263 is either held or interrupted per the management guidelines in Section 6.7.1 and Section 6.7.2.

All platelet count measurements obtained during Cycle 1 through Cycle 4 in the Phase 1 portion of the study will be either entered immediately on the eCRF or faxed to the Oncology Safety Management Team within 24 hours of report availability via the contact information provided in Section 6.5.

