Every effort should be made to obtain all ECGs approximately 4-8 hours post-dose (however, 6-8 hours post-dose is preferred), and if possible at approximately the same time of day. If pharmacokinetic data indicates the C_{max} of parent drug or a major metabolite occurs at a time different than this specified range, the timing of the ECG may be modified. A qualified physician will sign and date the ECGs, determine if any findings outside normal physiological variation are clinically significant (in consultation with a

cardiologist, if necessary) and document this on the appropriate CRF. The original ECG tracing with physician assessment will be retained in the subject's records at the study site and a copy will be faxed to the Oncology Safety Management Team within 24 hours of report availability via the contact information provided in Section 6.5. The ECG measurement obtained at Screening will be used to document baseline status of the subject so that safety comparisons can be made, if necessary. Repeat ECGs will be performed whenever clinically necessary.

12-Lead Electrocardiogram (ECG) (Phase 2a)

A 12-lead resting ECG will be performed for all subjects in Phase 2a at the following visits:

- Screening
- Cycle 1 Day 15
- Cycle 5 Day 1
- Cycle 9 Day 1
- Final Visit

For the Extension Study, a 12-lead resting ECG will be performed at the Final Visit.

If necessary, ECGs may be performed within 3 days of the visit, except Screening, which must be performed within 14 days prior to study drug administration.

The test results will be assessed for each subject on an ongoing basis by the AbbVie Medical Monitor and an independent cardiology expert, and monitoring may be adjusted depending on the observation of any clinically significant findings.

Every effort should be made to obtain all ECGs approximately 4-8 hours post-dose (however, 6-8 hours post-dose is preferred), and if possible at approximately the same time of day. If pharmacokinetic data indicates the C_{max} of parent drug or a major metabolite occurs at a time different than this specified range, the timing of the ECG may be modified. A qualified physician will sign and date the ECGs, determine if any findings

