outside normal physiological variation are clinically significant (in consultation with a cardiologist, if necessary) and document this on the appropriate CRF. The original ECG tracing with physician assessment will be retained in the subject's records at the study site and a copy will be faxed to the Oncology Safety Management Team within 5 days of report availability via the contact information provided in Section 6.5. The QT, QTc and heart rate will be recorded for all ECGs on the eCRF. The ECG measurement obtained at Screening will be used to document baseline status of the subject so that safety comparisons can be made, if necessary. Repeat ECGs will be performed whenever clinically necessary.

2D Echocardiogram with Doppler (Phase 1)

A 2D echocardiogram with Doppler will be performed for all subjects in the first 2 cohorts at Screening, Day 1 and Day 14 of Cycle 1, Day 1 of each subsequent cycle and at the Final Visit. For subsequent cohorts, an echocardiogram with Doppler will be performed at Screening, Day 1 and Day 14 of Cycle 1, Day 1 and Day 14 of Cycle 3 and at the Final Visit. If necessary, the Cycle 1 Day 14 and Cycle 3 Day 14 echocardiograms may be performed within 3 days prior to Day 14. During the lead-in period, an echocardiogram will also be performed on Lead-in Day 1. For the Extension Study, a 2D echocardiogram with Doppler will be performed at the Final Visit.

The test results for each subject will be assessed on an ongoing basis by the AbbVie Medical Monitor and an independent cardiology expert, and monitoring may be adjusted depending on the observation of any clinically significant findings.

Every effort should be made to obtain all echocardiograms approximately 4-8 hours post-dose (however, 6-8 hours post-dose is preferred), and if possible at approximately the same time of day. If pharmacokinetic data indicates the C_{max} of parent drug or a major metabolite occurs at a time different than this specified range, the timing of the echocardiogram may be modified. A qualified physician will sign and date the echocardiogram reports, determine if any findings outside normal physiological variation are clinically significant and document this on the appropriate CRF. The original

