Analyses of mean change from baseline in continuous vital signs variables which are measured longitudinally were performed (systolic blood pressure, diastolic blood pressure, heart rate, weight, and temperature). For each change from baseline analysis, the following summary statistics were presented: sample size, baseline mean, visit mean, and the mean, standard deviation, and minimum/maximum of the changes from baseline. The baseline and visit means were calculated for each visit for subjects who have both a baseline and visit value.

Assessment of Potentially Clinically Significant Vital Signs Values

For selected vital signs variables, a listing of all observations collected was generated for subjects that had at least one post-baseline observation meeting pre-defined criteria for potentially clinically significant values. The number and percentage of subjects who have at least one post-baseline observation meeting the pre-defined criteria for potentially clinically significant values was provided for each variable.

Pre-defined criteria for potentially clinically significant vital signs values are given in Table 4 below based on CTCAE criteria:

Table 4. Criteria for Potentially Clinically Significant Laboratory Values – Vital Signs Variables

Vital Signs Variables	Criterion	Definition of Potentially Clinically Significant
Systolic blood pressure	High	Value > 150 mmHg
Diastolic blood pressure	High	Value > 100 mmHg
Heart Rate	Low	Value \leq 50 bpm
	High	Value \geq 120 bpm
Temperature	Low	Value \leq 36°C
	High	Value \geq 38.5°C

Analysis Conventions

Definition of Baseline

The baseline value was defined as the last non-missing measurement collected before the first dose of navitoclax.

Definition of Final Observation

The final observation (Final Visit) was defined as the last non-missing observation collected within 30 days following the last dose of navitoclax.

Definition of Rx Days (Days Relative to the First Dose of navitoclax)

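### SAP Table 4 flags blood pressure only when it is high, and Phase 1 blood pressure is read hours before the ECG/echo window, so a clean table says little about falls or about peak exposure

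*Protocol*

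**What the plan says.** **Flags.** In the SAP section on potentially clinically significant vital signs, "Pre-defined criteria for potentially clinically significant vital signs values are given in Table 4 below based on CTCAE criteria". The systolic criterion is "Value > 150 mmHg" and the diastolic one is above 100 mmHg; both are labelled High and neither has a Low counterpart. Heart rate and temperature each have a Low and a High row. A subject is counted, and has observations listed, only if at least one post-baseline value meets a criterion. Protocol 8.1.4 says that vital signs will be judged against criteria developed by the sponsor; those criteria are not reproduced.

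**Timing.** Under Vital Signs, Protocol 5.3.1.1 says: "In Phase 1, blood pressure and pulse rate will be measured approximately 30 to 60 minutes after study drug administration". No reason is given for that interval. For the Phase 1 ECG the same section says "Every effort should be made to obtain all ECGs approximately 4-8 hours post-dose (however, 6-8 hours post-dose is preferred", and for the Phase 1 echocardiogram "Every effort should be made to obtain all echocardiograms approximately 4-8 hours post-dose". The ECG window is tied to Cmax: if the Cmax of the parent drug or a major metabolite "occurs at a time different than this specified range, the timing of the ECG may be modified", and the echocardiogram has a matching rule. Vital signs have no such rule. On Cycle 1 Days 1 and 14, Phase 1 pharmacokinetic samples are drawn pre-dose and at "2, 4, 6, 8 hours post-dose" (Protocol Table 4).

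**Background.** Protocol 3.0 reports that "ABT-263 caused increases in pulmonary and peripheral vascular resistance and decreases in cardiac output in the dog", without an increase in blood pressure. The effect was seen at a mean Cmax of 16.6 µg/mL, and there was no statistically significant change at 11.4 µg/mL.

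**The concern.** The SAP's threshold analysis looks at blood pressure in one direction only. The animal finding is lower cardiac output with no pressure rise, so the documents give no reason to watch for rises alone. A reader who sees no flagged blood-pressure values could take that as reassurance about falls, which the table was never able to report.

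The timing adds a second limit. The protocol treats the Cmax window as the relevant time for cardiac assessment but reads Phase 1 blood pressure and pulse well before it. Both the change-from-baseline summaries and the flag counts therefore describe exposure before the peak. The risk is one of interpretation: a clean Phase 1 blood-pressure table read as no effect at peak.

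**Working it through.** The plan gives no figure to reproduce here. The check sets the criteria side by side, does the clock arithmetic, and runs an illustrative concentration model.

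**1. Criteria in SAP Table 4**

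| Variable | Low | High |
|---|---|---|
| Systolic pressure | none | > 150 mmHg |
| Diastolic pressure | none | > 100 mmHg |
| Heart rate | ≤ 50 bpm | ≥ 120 bpm |
| Temperature | ≤ 36 °C | ≥ 38.5 °C |

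Six of the eight cells are filled. The two empty ones are the low limits for blood pressure. Followed as written, no fall in pressure can bring a subject into the count or the listing.

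**2. Clock gap**

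- Blood pressure at 0.5-1 h against ECG/echo at 4-8 h: shortest 4 − 1 = 3 h, longest 8 − 0.5 = 7.5 h.
- Against the preferred 6-8 h: 6 − 1 = 5 h to 8 − 0.5 = 7.5 h.
- First post-dose concentration at 2 h: 2 − 1 = 1 h to 2 − 0.5 = 1.5 h after the reading, so no scheduled sample matches it.

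**3. Illustrative concentration at the reading**

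The documents give neither a human time to peak nor a human half-life. Assumed: Tmax 4, 6 or 8 h (from the ECG/echo window); half-life 4.6 or 8.4 h (the animal range in Protocol 3.0), plus 20 h as a wide upper value with no source in the documents.

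One-compartment oral model: ke = ln 2 / half-life; ka solves ln(ka/ke)/(ka − ke) = Tmax. First dose: C(t) is proportional to [e^(−ke·t) − e^(−ka·t)]/(ka − ke). Steady state, dosing every 24 h: divide the first exponential by (1 − e^(−24·ke)) and the second by (1 − e^(−24·ka)). Each value is then divided by the curve's own maximum.

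Example, half-life 4.6 h and Tmax 8 h: ke = 0.151, ka = 0.102. The absolute difference of the exponentials is 0.950 − 0.927 = 0.023 at 0.5 h and 0.442 − 0.300 = 0.143 at 8 h, a ratio of 0.16.

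| Half-life (h) | Tmax (h) | First dose, 0.5 h / 1 h | Steady state, 0.5 h / 1 h | Steady-state pre-dose |
|---|---|---|---|---|
| 4.6 | 4 | 31% / 54% | 37% / 58% | 8% |
| 4.6 | 6 | 21% / 38% | 37% / 52% | 19% |
| 4.6 | 8 | 16% / 30% | 49% / 59% | 38% |
| 8.4 | 4 | 33% / 57% | 49% / 68% | 22% |
| 8.4 | 6 | 22% / 40% | 46% / 60% | 30% |
| 8.4 | 8 | 16% / 31% | 51% / 61% | 40% |
| 20 | 4 | 39% / 63% | 71% / 84% | 51% |
| 20 | 6 | 25% / 45% | 68% / 78% | 55% |
| 20 | 8 | 19% / 34% | 69% / 76% | 60% |

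The range is 16-63% of peak after a first dose and 37-84% at steady state. With the animal half-lives alone it is 16-57% and 37-68%. At 4-8 h the same model gives at least 75% of the steady-state peak. The readings are below peak in every scenario.

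**4. Exposure context**

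Protocol 3.0 simulates a human Cmax of about 6.5 µg/mL at 350 mg. The dog effect level is 16.6/6.5 = 2.6 times that, and the level without significant change is 11.4/6.5 = 1.8 times. At the Phase 2a dose of 250 mg, assuming proportionality, Cmax is 6.5 × 250/350 = 4.6, and the ratios are 3.6 and 2.5.

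**The case against.** A reader might infer that the plan will miss a predicted haemodynamic effect. The documents do not support that:

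- The effect is a dog finding, at Cmax values above the simulated human one. No passage predicts a fall in human blood pressure, and the dog text reports neither a rise nor a fall.
- A cuff reading does not measure cardiac output. Phase 1 has Doppler echocardiography aimed at 4-8 h, with ongoing review by the medical monitor and an independent cardiology expert (Protocol 5.3.1.1).
- The SAP also reports the mean, SD, minimum and maximum change from baseline in blood pressure, so a fall at the measured time would show there. Protocol 6.1.1 allows a vital-sign change to be recorded as an adverse event.
- The readings are not at trough. At 60 minutes the steady-state model gives 52-84% of peak, against 8-60% pre-dose.
- The 30-60 minute reading may serve some other purpose, and the SAP reports all 29 Phase 1 subjects as already treated, so there is little left to reschedule.

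All of this stands and limits the point. None of it supplies a low limit. A minimum change is one number per visit and does not say how many subjects had a low value or who they were. The echo safeguard is also weaker in analysis than in collection: Protocol 8.1.4 plans trend analyses of echo and ECG, but the SAP text describes neither, only adverse-event searches for cardiac failure and pulmonary hypertension.

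The 30-60 minute rule also does not describe every visit. Footnotes to Protocol Tables 1 and 2 let procedures other than platelet counts be done up to 72 hours before Day 1 of a cycle, which on the 14/21 schedule is in the off-drug week. Those passages need to be reconciled before the readings are labelled.

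**Conclusion.** The point holds as a gap in safety reporting that is cheap to close. Both low blood-pressure cells of SAP Table 4 are empty, so the threshold analysis cannot report a fall of any size; this rests on the text alone. Phase 1 blood pressure and pulse are read 3 to 7.5 h before the ECG/echo window and are pre-peak; the gap is plain arithmetic. The 16-63% and 37-84% figures are illustrative, because they depend on an assumed Tmax, half-life and one-compartment model.

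The point does not extend to a claim that an expected human effect will go undetected, or that high-only flags look in a direction shown to be wrong. Echocardiography remains the main measure of the haemodynamic effect.

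**What to change.** 1. Add Low rows for systolic and diastolic pressure to SAP Table 4, taken from the sponsor's vital-sign criteria cited in Protocol 8.1.4. Count and list the subjects who meet them, and mark the criterion as added after the fact. If those criteria hold no low limit, the sponsor should say so and justify the one it uses.
2. For Phase 1 data already collected, state the planned time since dose (the actual time where recorded) and label the values pre-peak. Identify readings taken before dosing under the 72-hour allowance. Do not present a clean blood-pressure table as evidence of no effect at peak.
3. For any further in-clinic dosing of the Phase 1 type, take a blood pressure and pulse reading at the ECG/echo time. Subjects are already in clinic up to the 8-hour sample on Cycle 1 Days 1 and 14.

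Cost: two table rows, a footnote, and one reading at an existing visit. The downsides are a few more flagged values, a post hoc criterion, and readings at different times after dosing that cannot be compared directly.

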5.3.1.2 Meals and Dietary Requirements

Subjects will self-administer ABT-263 orally once daily (QD) within 30 minutes following the completion of breakfast, unless otherwise specified. Subjects may not

consume grapefruit or grapefruit products within the 3-day period prior to initial study drug administration and until the last treatment cycle is completed due to possible CYP3A mediated metabolic interaction.

5.3.1.3 Blood Samples for Pharmacogenetic Analyses

DNA

All Sites

Phase 1 and 2a: Optional

One 4 mL blood sample for DNA isolation will be collected at Screening (preferred) or prior to treatment on Lead-in Day 1 (21/21 day dosing schedule) or Cycle 1 Day 1 (14/21 day dosing schedule) from each subject who consents to provide samples for pharmacogenetic analysis. The collection, processing, and shipping of the specimens should be performed as described in the M06-873 laboratory manual.

Samples will be shipped to AbbVie for DNA extraction and long-term storage. AbbVie or a designated laboratory will store the DNA samples in a secure storage space with adequate measures to protect confidentiality.

If pharmacogenetic testing is performed, results from individual subjects will be kept coded and confidential. Samples will be coded so that subject identities will not be available to the scientists conducting the genotyping analysis. The samples will be retained while research on ABT-263 or Bcl-2 inhibitors continues. Upon completion of the research, the samples will be destroyed.

